4.2 Interim Analysis

Interim analyses will be conducted on an as-needed basis in order to support regulatory activities. Two interim analyses were conducted. The first interim analysis supported the Biologic License Application (BLA) and the second interim analysis supported the 120 day safety update. The results of interim analyses were not intended to be used to stop or adapt the study.

The analysis for the first and the second interim analyses are described in two interim SAPs, dated 19Jan2016 and dated 21Jun2016, respectively.

4.3 Disposition of Subjects

The following will be presented in summary tables for all subjects who provide informed consent/assent (as appropriate) by treatment (40 IU/kg CSL830; 60 IU/kg CSL830 and ≥ 40 IU/kg CSL830 [i.e., combined treatment groups]) and overall:

- The number of subjects who provide consent/assent (as appropriate).
- The number of subjects who undergo Screening.
- The number of “CSL830- Continuation” Subjects.
- The number of “CSL830-Interrupted” Subjects.
- The number of “CSL830- Naïve” Subjects
- The number of subjects who are not allocated to a treatment.
- The number of subjects who are randomized.
- The number of subjects who participate in the Extension Period.
- The number of subjects who undergo no CSL830 dose increase in Treatment Period 1
- The number of subjects who undergo no CSL830 dose increase in Treatment Period 2
- The number of subjects who undergo no CSL830 dose increase in the Extension Period
- The number of subjects who undergo no CSL830 dose increase in Treatment Period 1 and Treatment Period 2
- The number of subjects who undergo no CSL830 dose increase in Treatment Period 2 and the Extension Period
- The number of subjects who undergo no CSL830 dose increase in in any Period
- The number of subjects who undergo 1 CSL830 dose increase in Treatment Period 1
- The number of subjects who undergo 1 CSL830 dose increase in Treatment Period 2

- The number of subjects who undergo 1 CSL830 dose increase in the Extension Period
- The number of subjects who undergo 1 CSL830 dose increase in Treatment Period 1 and Treatment Period 2
- The number of subjects who undergo 1 CSL830 dose increase in Treatment Period 2 and the Extension Period
- The number of subjects who undergo 1 CSL830 dose increase in any Period
- The number of subjects who undergo 2 CSL830 dose increases in Treatment Period 1
- The number of subjects who undergo 2 CSL830 dose increases in Treatment Period 2
- The number of subjects who undergo 2 CSL830 dose increase in the Extension Period
- The number of subjects who undergo 2 CSL830 dose increases in Treatment Period 1 and Treatment Period 2
- The number of subjects who undergo 2 CSL830 dose increases in Treatment Period 2 and the Extension Period
- The number of subjects who undergo 2 CSL830 dose increases in any period
- The number of subjects who completed the study
- The number of subjects who discontinued participation in the study (overall and for Period 1, 2 and the Extension Period; including the reason for discontinuation).

For detail of the definition of completers and non-completers see [Section 3.5](#).

Percentages are based on the number of subjects randomized/enrolled in each group. The percentages of subjects who underwent screening, "CSL830-Continuation", "CSL830-Interrupted" and "CSL830-Naive" Subjects as well as the percentage of the subjects randomized into the study are based on the number of subjects who provided informed consent/assent. Percentages for the reason for discontinuation are based on the number of subjects discontinued in each group.

The number of subjects in each analysis population will be summarized by treatment (40 IU/kg CSL830; 60 IU/kg CSL830; ≥ 40 IU/kg CSL830 and overall). Subjects in the ITT, the PP and the CCI will be assigned to treatment as randomized and subjects in the Safety Population, the CCI will be assigned to treatment as treated and will be assigned to all doses they have received during the study.

A by-subject listing will be produced including the assignment of subjects to analysis populations.

Disposition data (including the reason for discontinuing use of CSL830 or withdrawing from the study) will be listed by site and subject. All Screen Failures will be listed.

4.4 Baseline and Demographic Characteristics

Subject characteristics and medical history will be presented in summary tables for the ITT and Safety Populations as described in [Section 4.1](#).

This will include:

- Demographics (age [years], sex, race, ethnicity, height, body weight, and body mass index [BMI; calculated as kg/m²]).
- Medical history (relevant medical history for the previous 6 months, contraception method [if relevant]) and the correspondent therapies which have an end date on or after the date of the first study treatment (current therapies). Medical history will be presented by system organ class (SOC) and preferred term (PT), and will be classified using version 18.0 of the Medical Dictionary for Regulatory Activities (MedDRA). Current Therapies will be presented by Anatomical Therapeutic Chemical (ATC) class and PT.
- HAE history (including confirmation of HAE diagnosis, identification of HAE type, and number of HAE attacks in the 3 months before the Screening visit) and Medical HAE History (any prior prophylactic therapy relating to HAE during previous 3 months for “CSL830-Naïve” Subjects).

The relevant medical history for the previous 6 months will include all medical history of subjects during the previous 6 months before Screening. The confirmation of HAE diagnosis, identification of HAE type, and number of HAE attacks in the 3 months before Screening will be presented.

The number of HAE attacks in the 3 months before the Screening Visit will also be displayed as the rate of HAE attacks before the Screening Visit per month. Therefore, the number of HAE attacks in the 3 months before the Screening Visit will be divided by 3.

For “CSL830-Naïve” Subjects and “CSL830-Interrupted” Subjects screening is the Screening Visit of study CSL830_3002. For “CSL830-Continuation” Subjects, screening is the Screening Visit of study CSL830_3001. Information in the medical history will be updated if any changes occurred in the course of study CSL830_3001.

The label “Any Prior Prophylactic Therapy Related to HAE During Previous 3 Months” in the HAE history and medical HAE history table will only include therapies taken within 3 months prior to Screening of Study CSL830_3002. Prior therapies before Screening of study CSL830_3001 will not be included. Consequently, only “CSL830-Naïve” Subjects will have data in this part of the table.

Summaries of demographics, medical history, current therapies, HAE history, Medical HAE History will also be presented for the following subgroups:

- Roll over classification (“CSL830-Continuation” Subjects, “CSL830-Interrupted” Subjects, and “CSL830- Naïve” Subjects).

A by-subject listing of demographic characteristics, baseline characteristics, and medical history will also be presented.

Extent of exposure and treatment compliance will be calculated as described below and will be listed and summarized descriptively as described in [Section 4.1](#).

4.4.1 Extent of exposure

Exposure will be summarized using the Safety Population. The duration of exposure per subject (presented in years and weeks) will be summarized in 3 ways to support the 3 approaches to the analysis of the primary safety endpoint of person time incidence rates:

1. by treatment group, as treated, up to CSL830 dose increase or either CSL830 discontinuation or study completion – whichever comes first, i.e., the duration (years or weeks) of exposure per subject is equal to (the subject's first dose increase or discontinuation or completion visit [whichever comes first] – the subject's start date in this treatment + 1) / 365.25 [for weeks it will be divided by 7].
2. by treatment group, as treated at the time of randomization, up to CSL830 discontinuation or study completion – whichever comes first, i.e. the duration (years or weeks) of exposure per subject is equal to (the subject's study discontinuation date or study completion date – the subject's start date in the study + 1) / 365.25 [for weeks it will be divided by 7]. Subjects accrue exposure based upon their initial treatment until stopping CSL830; regardless of any dose increase.
3. by actual treatment. The duration (years or weeks) of exposure per subject is equal to (the subject's end date in the treatment – the subject's start date in this treatment + 1) / 365.25 [for weeks it will be divided by 7]. Subjects accrue exposure by treatment dose over the duration they receive each treatment dose while participating in the study, e.g. a subject randomized to 40 IU/kg and up-titrated to 60 IU/kg will be displayed in both treatments and in ≥ 40 IU/kg with their corresponding duration in that treatment.

Depending on the analysis approach, a subject's start date in a treatment will correspond to the first visit date or the date of dose increase. A subject's end date is the date of discontinuation, study completion, or the date of dose increase – 1. For subjects who are not taking part in the Extension Period, the date of study completion is the date of the Week 53 Visit and for subjects who are taking part in the Extension Period, the date of study completion is the date of the Week 88 Visit. If a subject discontinued from the study, the date the subject came back to site for a final study visit will be entered as the date of discontinuation (to be entered as Week 53 Visit for subjects not taking part in the Extension Period and entered as Week 88 Visit for subjects taking part in the Extension Period) or if no further study visit takes place, the date when the subject informed the investigator.

The time between the Week 53 Visit and the Follow-up Visit of Treatment Period 2 will not be included in the duration of exposure for subjects who are not taking part in the Extension Period. For subjects who are taking part in the Extension Period, a rest period will not be included in the duration of exposure. For subjects who are taking part in the Extension Period, the time between the Week 88 visit and the Follow-up Visit of the Extension Period will not be included in the duration of exposure.

A by-subject listing will be produced displaying all study drug injections.

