3.3 Planned Study Duration

Treatment Period 1 and Treatment Period 2

The duration of the study for an individual subject is expected to be up to 58 weeks. This estimation is based on:

- A Screening Period lasting up to 4 weeks (≤ 28 days), as needed.
- Two treatment periods totaling 52 weeks (367 days \pm 2 days).
- A Follow-up Period lasting 2 weeks (14 days \pm 3 days).

The overall study duration (ie, from the first subject’s first Screening Visit to the last subject’s Follow-up Visit) is planned to be 26 months, but will depend on recruitment.

Extension Period (Optional)

The Extension Period (88 weeks) followed by the Extension Period follow-up (2 weeks) will begin at first subject first visit in the Extension Period and result in an anticipated total study duration of up to approximately 146 weeks for participating subjects. Subjects who have any Extension Period visits that occur within 6 weeks before the study end date will be handled as completers. These subjects will attend the final study visit (Extension Period Week 88) in place of their next study visit or telephone contact and will receive follow-up telephone contact (Extension Period Week 90 ± 3 days). Subjects who roll-over into the Extension Period prior to the Treatment Period 2 Follow-up Visit will be regarded as completers. All subjects who are not withdrawn from the study will be considered completers of the study.

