4.2.2 Procedures for Handling Withdrawals

If a subject declines further participation or is withdrawn from the study, attempts will be made to complete and document the assessments scheduled for the last visit in Treatment Period 2 (ie, the Week 53 Visit) (see [Section 8.4.4.7](#)) or the last visit in the Extension Period (Extension Period Week 88)(see [Section 8.4.6.20](#)). These subjects will then attend a Follow-up Visit occurring 14 days (\pm 3 days) after a visit resulting in study discontinuation, unless informed consent/assent has been withdrawn (see [Section 8.4.5.1](#)). If the subject is withdrawn from the study after receiving CSL830, every effort will be made to ensure that the relevant safety assessments are completed. The subject may also be asked by the investigator to complete other study assessments.

If the subject withdraws from the study, and also withdraws consent/assent (as appropriate) for disclosure of future information, CSL may retain and continue to use any data collected before such withdrawal of consent/assent (as appropriate).

In the event that a subject withdraws from the study, the investigator should record the reason and date of withdrawal in the electronic case report form (eCRF) and in the subject's medical records.

Subjects who discontinue or withdraw from Treatment Periods 1 or 2 will not be eligible to participate in the Extension Period.

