4.7.1 Primary Safety Analysis

Primary safety endpoints are listed in [Section 2.1](#).

The date of study completion is defined for the safety analyses as the (latest) Follow-up Visit. If a subject discontinued from the study, the date the subject came back to site for a final

study visit will be entered as the date of study discontinuation (to be entered as Week 53 Visit for subjects not taking part in the Extension Period and to be entered as Week 88 Visit for subjects taking part in the Extension Period) or if no further study visit takes place, the date when the subject informed the investigator. The study completion or study discontinuation (whichever applies for the individual subject) is considered as the end of treatment date.

The person-time incidence rates will be calculated in two different ways:

- For the number of subjects experiencing a particular event (bullet points i. below),
- For the number of experienced events (bullet points ii. below).

These 2 analyses approaches for the primary safety endpoints are conducted using 3 different approaches for the selection of the treatment groups which are included in the respective analyses. The following treatment groups will be regarded:

- 1) Treatment, as treated, up until CSL830 dose increase, or either CSL830 discontinuation or study completion – whichever comes first.
- 2) Treatment, as treated at the time of randomization, up to CSL830 discontinuation or study completion – whichever comes first.
- 3) Actual treatment.

In total, six analyses will result and the person-time incidence rates will be calculated

for 1) as

- i. the number of subjects experiencing a given primary endpoint safety event during the treatment duration with CSL830 up until the time of CSL830 dose increase or either CSL830 discontinuation or study completion (whichever is first), divided by the sum of each subject's time at risk. The "time at risk" (in years) is calculated per subject as:

(Date the subject experiences the first event or a CSL830 dose increase or either CSL830 discontinuation or study completion (whichever is first) – date of the subject's first injection of CSL830 in treatment + 1) / 365.25.

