4.7.2.3 Analysis of Laboratory Findings

Normal ranges will be provided for laboratory tests. Values outside the normal range will be judged as clinically significant or non-clinically significant by the investigator. All abnormal laboratory data considered as clinically significant will be presented as AE.

All continuous laboratory parameters will be plotted against their scheduled assessments visits.

Analyses of haematology, biochemistry, and coagulation parameters will consist of the following:

- Descriptive statistics for baseline and each treatment visit, including changes from baseline to each treatment visit
- Mean values and the SD of the continuous laboratory parameters at each scheduled visit will be plotted against scheduled visits.

Baseline will be the assessment before the first injection (Week 1 Day 1) for all “CSL830-Naïve” and “CSL830-Interrupted” Subjects and “CSL830-Continuation” Subjects who did not complete the assessments at the CSL830_3001 End of Study Visit. For “CSL830-Continuation” Subjects who complete the assessments at the CSL830_3001 End of Study Visit, these assessments will be the baseline. If the baseline value for a subject is missing, no change from baseline will be calculated for the subject.

The number and percentage of subjects without anti-C1-INH antibodies and with anti-C1-INH antibodies (inhibitory, non-inhibitory and inhibitory and non-inhibitory combined) during the study will be summarized overall and for each study visit

Urinalysis, viral serology and pregnancy testing results will be listed only.

Notes:

- All results outside predefined normal ranges will be flagged as high or low in the data listings.
- Clinically significant laboratory values will be flagged in the listings.
- Unscheduled results will be listed only and not included in summary tables.

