4.7.3 Vital Signs and Body Weight

Results of vital signs and body weight will be summarized by visit. Descriptive statistics for baseline and each treatment visit will be displayed. Descriptive subgroup analysis will be done for subjects who use any oral Prophylaxis for Treatment of HAE during the study.

Baseline will be Week 1 Day 1 for all “CSL830-Naïve” and “CSL830-Interrupted” Subjects and “CSL830-Continuation” Subjects who did not complete the assessments at the CSL830_3001 End of Study Visit. For “CSL830-Continuation” Subjects who complete the assessments at the CSL830_3001 End of Study Visit, these assessments will be the baseline. All vital signs and body weight data will be listed and abnormal results will be flagged.

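### Early-termination and early-closure assessments are labelled Week 53 or Extension Week 88, and the by-visit secondary safety tables have no actual-day rule to separate them

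*SAP*

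**What the plan says.** **Entry rule.** SAP 4.4.1 records the final visit of a discontinued subject who returns to site as "to be entered as Week 53 Visit for subjects not taking part in the Extension Period and entered as Week 88 Visit" for those in the Extension. SAP 4.7.1 repeats the rule, using the Week 53 label "for subjects not taking part in the Extension Period and to be entered as Week 88 Visit" for those who are. If the subject does not return, only a date is recorded.

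**Withdrawal procedure.** Protocol 4.2.2 matches this. When a subject leaves, "attempts will be made to complete and document the assessments scheduled for the last visit in Treatment Period 2", or those of the last Extension visit, at whatever time that happens.

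**Early closure of the Extension.** Protocol 3.3 treats subjects with an Extension visit in the 6 weeks before the study end date as completers, and adds: "These subjects will attend the final study visit (Extension Period Week 88) in place of their next study visit or telephone contact".

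**Tables.** For haematology, biochemistry and coagulation, SAP 4.7.2.3 plans "Descriptive statistics for baseline and each treatment visit, including changes from baseline to each treatment visit", and plots means against scheduled visits. Antibody status "during the study will be summarized overall and for each study visit". SAP 4.7.3 says: "Results of vital signs and body weight will be summarized by visit". SAP 4.7.5 counts subjects at or above the DVT and PE score thresholds at each visit.

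**What the labels mean.** The schedules place Week 53 at Day 367 (± 2 days) and Extension Week 88 at Extension Day 617 (± 2 days). Protocol 8.4.4.7 puts the Week 53 Visit at least 365 days after randomization.

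**The concern.** One visit name covers two kinds of record: assessments made on schedule, and assessments made whenever a subject left or the Extension closed. A subject who withdraws at Week 10 and returns to site supplies values to the Week 53 column. For antibodies this can be the subject's only post-baseline result, because in the main periods sampling is scheduled only on Day 1, at Week 25 and at Week 53.

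Long-term safety is the primary objective, and readers will look to the last column of each treatment phase for antibody prevalence, coagulation markers and liver enzymes. Early leavers may also differ from those who stay, since some leave because of an adverse event. Their values would enter the one-year column, and nothing in the table would show it.

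**Working it through.** **1. Is there a rule that separates the records?** The SAP's visit-level exclusion is in 3.3.4, repeated for laboratory results in 4.7.2.3: unscheduled measurements are listed but not tabulated. A final visit entered as Week 53 or Week 88 is not unscheduled, so it is tabulated. The SAP text has no visit window, no early-termination row and no mapping by actual day.

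**2. Which tables are touched?**
- Week 53: haematology, biochemistry, coagulation, antibodies, vital signs and weight, DVT/PE scores.
- Extension Week 88: ALT/AST, coagulation, antibodies, vital signs and weight, DVT/PE scores. Protocol 8.4.6.22 lists no haematology there.
- Not touched: urinalysis and viral serology, which SAP 4.7.2.3 only lists.
- Not touched: exposure (SAP 4.4.1) and the primary person-time rates (SAP 4.7.1), which are computed from dates.

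**3. The plan's own figures.** Protocol 3.5 gives about 110 randomized, up to 10% withdrawal and 100 completers: 110 × 0.90 = 99, which agrees. Durations: 4 + 52 + 2 = 58 weeks and 4 + 52 + 88 + 2 = 146 weeks, both as stated. Extension Week 88: 88 × 7 + 1 = Day 617, as stated.

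**4. Size at Week 53.** Withdrawals: 110 × 0.10 = 11, leaving 99 true Week 53 records.
- All return to site: 11 / 110 = 10.0% of the column.
- Half return: 5.5 / (5.5 + 99) = 5.3%.

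Mean time on study in the column is (e × m + 99 × 52) / (e + 99), where e is the number returning and m their mean week of leaving (assumed):

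| m (weeks) | all return, e = 11 | half return, e = 5.5 |
|---|---|---|
| 13 | 48.1 | 49.9 |
| 26 | 49.4 | 50.6 |
| 39 | 50.7 | 51.3 |

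**5. Size at Extension Week 88.** No study end date is given, so this is an illustration. Assume closure 88 weeks after the first Extension entry and uniform entry over W weeks. For the upper W, take the 26-month overall plan less one subject's 58 weeks: 26 × 30.4375 / 7 − 58 = 113 − 58 = 55 weeks. For the lower W, assume 26 weeks. Mean Extension time is 88 − W/2, and the minimum is 88 − W.
- W = 26: mean 75 weeks, minimum 62.
- W = 55: mean about 60 weeks, minimum 33.

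All of these subjects have already had 52 weeks of treatment. The lowest case is 52 + 33 = 85 weeks in total, against a nominal 52 + 88 = 140.

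**The case against.** The case for leaving this alone has real substance.

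- **The primary analysis is sound.** All seven primary endpoints, antibodies included, are rates over actual time at risk. A reader might infer that the labelling biases the trial's main safety result. It does not.
- **The signal is carried elsewhere.** Clinically significant laboratory values are presented as adverse events, adverse events leading to discontinuation are tabulated by start date, and antibodies are also summarized overall. Only descriptive by-visit tables and plots are affected.
- **Week 53 is mostly right.** A reader might infer that the column does not hold one-year data. On the planned withdrawal, about 90% or more of its records are true Week 53 data.
- **Extension Week 88 is not short exposure.** A reader might take an early-closed subject for one with little treatment. Every Extension subject has completed the 52-week treatment periods, so even the lowest illustrative case is about 85 weeks.
- **The Extension arithmetic is conjecture.** A reader might conclude that most Week 88 records are far off time. A common closing date is one reading of Protocol 3.3. The 55-week span comes from a global plan said to depend on recruitment, and it is applied here to roughly 12 US sites.

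All five points stand, and they limit the finding. Two further replies carry less weight. SAP 4.11 allows individual visits to be excluded after data review, but only for protocol deviations; a withdrawal visit done under Protocol 4.2.2 is not a deviation in itself. The table shells are a separate document and could remap visits, but the SAP does not call for it.

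**Conclusion.** The point holds for the by-visit secondary safety tables and plots, and only for those. Followed as written, the plan puts early-termination data in the Week 53 column, and early-termination and early-closure data in the Extension Week 88 column, without marking either.

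At Week 53 the ceiling is about 11 of 110 records, or about 5% if half of the withdrawals return to site. This rests on the planned 10% withdrawal. At Extension Week 88 the share may be larger, but the documents do not allow it to be sized. The 75-to-60-week means depend wholly on the assumed closing date and uniform entry.

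The change is worth making because the correction is cheap and these columns will be read as long-term data. It does not call the primary safety results into question.

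**What to change.** In SAP 4.7.2.3, 4.7.3 and 4.7.5:

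1. Include an assessment in the Week 53 column only if its actual study day falls within a stated window around Day 367, and in the Extension Week 88 column only if it falls within a stated window around Extension Day 617.
2. Show all other early-termination and early-closure assessments in a separate last on-treatment assessment row, with the number of subjects and the median and range of actual exposure.
3. Do not force these assessments to the nearest scheduled visit. That fails for sparse assays. An antibody sample at Week 40 is 15 weeks from Week 25 and 13 from Week 53, so it would still go to Week 53. In the readable text, Extension ALT/AST is scheduled at Weeks 48 and 88, so a Week 70 sample (22 and 18 weeks away) would still go to Week 88. A Week 30 antibody sample would collide with the subject's own Week 25 record.

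The cost is SAP wording, one variable derived from dates already collected, and a smaller n in the Week 88 column. No new data are needed and no observation is lost.
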